7.2.3.1. Physical Function

Short Physical Performance Battery (SPPB): The SPPB is an objective physical assessment evaluating lower extremity physical function.⁹⁶ It is comprised of a four-meter walk, repeated chair stands and a balance test. Impairment on SPPB testing has been shown to be predictive of short-term

mortality and nursing home admission in community-dwelling older adults. We will also perform the virtual SPPB via the phone/zoom, which evaluates the participants' perceived ability to perform above tests (walking, repeated chair stands, and balance).

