Cognition; Montreal Cognitive Assessment (MOCA): A 30-point cognitive screen test with excellent sensitivity for individuals with mild dementia and mild cognitive impairment. It can also be used to trend changes in cognitive status over time. If in-person assessment is not possible, MOCA-blind will be conducted via zoom/phone.

Comorbidity (baseline only); OARS Physical Health Section: Patients selfreport their coexisting medical conditions and also rate the degree to which their illness causes impairment in daily activities. The OARS Physical Health Section has been shown to correlate significantly with health professional ratings of comorbidity as well.

Social Support (baseline only); OARS Medical Social Support survey: A 13-question survey asking patients to identify the number of support persons involved in their medical care as well as the degree to which they felt supported in a variety of situations.

Medications (baseline only): We will record all prescription and nonprescription medications, dosage and frequencies from the medical records. Polypharmacy is defined as the use of 5 or more medications.

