The feasibility of the GO-EXCAP Mobile App will be evaluated based on the following: a) Percentage of patients wearing the activity tracker and entering resistance exercise data into the mobile app and b) Percentage of patients performing both walking and resistance exercises during the study period days. Recruitment rates (percentage of patients who are approached and agree to enroll) and retention rates (percentage of patients who are enrolled and complete post-intervention assessments) will also be described

We will consider the intervention feasible if 1) \geq 70% of patients wear the activity tracker and enter resistance exercise data into the mobile app on at least 50% of the study period days, and 2) \geq 70% of patients performed both walking and resistance exercises on at least 50% of the study period days. We chose these criteria based on our previous mobile app study¹⁶ and on published exercise studies in older patients with AML.^{29,30} We will report percentage of adherence with 95% exact confidence interval (CI) calculated by the Clopper-Pearson method. We anticipate that about 20-30% of the participants will withdraw before post-intervention assessment due to rapid disease progression or death. These patients will not be included in the feasibility analysis because their withdrawals from the study are not related to the intervention. With 25 patients enrolled we anticipate at least 17 patients to be evaluable for our feasibility aims. When we estimate the percentage of adherence, a 95% CI will span approximately +/- 25%. For example, if we observe 12/17 (71%) patients complete the tasks, the CI will be 44-90%.

We will also tabulate the recruitment rates, retention rates, and intervention usability, and collect the reasons patient decline to be enrolled. In addition, we will evaluate the distribution and describe the following measures using descriptive statistics: 1) activity levels, 2) physical function (SPPB/vSPPB), 3) fatigue (BFI), 4) depression (CES-D Scale), 5) quality of life (FACT-Leu), and 6) Other geriatric assessment measures. Differences in activity levels, physical function, fatigue, depression, quality of life, and other geriatric assessment measures between pre- and post-treatment will be assessed using paired t-tests or Wilcoxon signed rank tests. Anticipated sample size of more than 12 patients with baseline and follow-up data will be sufficient to obtain the preliminary estimates of the outcomes measures.^{115,116}

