9.0. DATA MANAGEMENT

9.1. Data Collection Table (Aim 2)

	SCHEDULE OF DATA COLLECTION			
	Eligibility and Consent Form	Baseline Assessment (week 0)	Mid- Intervention Assessment (week 3-5)	Post- intervention Assessment* (week 8± 4)
Written Informed Consent	X			
Demographics		X		
Cancer and Treatment Characteristics		X		
Qualitative Interview			Х	Х
Activity Levels (Activity Tracker)		Х		х
Exercise Habits and Readiness		Х		
Short Physical Performance Battery ^b /Virtual Short Physical Performance Battery		Х		Х
Brief Fatigue Inventory (BFI)		X		Х
Center for Epidemiologic Studies Depression Scale (CES-D)		Х		Х
Functional Assessment of Cancer Therapy-Leukemia (FACT-Leu)		Х		Х
Self-Efficacy for Exercise		X		Х
Actigraphy ^{b,d}		X		Х
Geriatric Assessment Measures • Activities of Daily Living		х		Х

 Instrumental Activities of Daily Living Fall History 6-Minute Walk Test^{b,d} Montreal Cognitive Assessment (MoCA or MOCA Blind) 		
Bioelectrical Impedance System ^{a.b,d}	X	Х
Handgrip Dynamometer ^{b,d}	X	Х
Muscle Strength Testing ^{a.b,d}	X	X
Heart Rate Variability ^{a,b,d}	X	X
Feasibility metrics		X
System Usability Scale		X
Complete blood count (from electronic medical record)	X	X
Blood samples ^b	X	X

^aIf patient elects to undergo the assessments at the cancer center instead of the Physical Exercise, Activity and Kinesiology laboratory, these assessments will not be conducted.

^bMay be omitted for patient safety (i.e., if in-person assessments are not possible)

dIf research activities are conducted at Wilmot affiliated sites, these assessments may be omitted

9.2. All hardcopy research records will be stored onsite in the URMC, in locked research files at the James P. Wilmot Cancer Center. The Cancer Center is secured with electronic key cards. Offices within the Cancer Center are again secured by key and data is kept in locked file cabinets. Electronic research records are stored on the URMC's password secured and firewall protected networks. These are the same methods of security used for patient medical records. All study data (including the electronic data kept by the PointClick Care company) will be kept for a period of 7 years after the study and all reports and publications are complete.

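### The pre-post tests do not require the same version at both visits: MoCA may be replaced by MoCA-blind, and SPPB and virtual SPPB are not clearly kept apart, so a change of mode can look like a change in the patient

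*Combined protocol and SAP*

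**What the plan says.** **Cognition.** Section 7.2.3.6 describes the MoCA as "A 30-point cognitive screen test" and gives a substitution rule: "If in-person assessment is not possible, MOCA-blind will be conducted via zoom/phone". The data collection table in 9.1 carries a single entry, "Montreal Cognitive Assessment (MoCA or MOCA Blind", among the geriatric assessment measures, marked at baseline and post-intervention.

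**Physical function.** Section 7.2.3.1 defines two different things. The in-person battery is performed: "The SPPB is an objective physical assessment evaluating lower extremity physical function". The virtual form is a report by the patient: "We will also perform the virtual SPPB via the phone/zoom, which evaluates the participants' perceived ability to perform above tests". Section 9.1 puts both in one row. A footnote there lets the in-person SPPB be omitted for patient safety, and 7.2.3 makes the same allowance for in-person assessments in general.

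**Analysis.** Section 8.2.2 lists the outcome as "physical function (SPPB/vSPPB" and the geriatric measures as a group. It then says that differences in these domains "between pre- and post-treatment will be assessed using paired t-tests or Wilcoxon signed rank tests".

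**What is not there.** No section asks for the same mode at both visits, limits the paired tests to same-mode pairs, puts MoCA and MoCA-blind on a common scale, or plans a sensitivity analysis by mode. The multiple imputation in 8.1.2 deals with missing values, not with values obtained by a different instrument.

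**The concern.** A paired test reads the within-patient difference as change over time. That holds only if the same quantity is measured twice. If the baseline is MoCA and the follow-up is MoCA-blind, the difference contains any offset between the versions as well as any change in the patient. The same would be true of a performed SPPB at one visit and a perceived-ability score at the other.

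There is no control arm in which a mode effect could cancel. The only documented reasons to go remote are patient safety and the impossibility of an in-person visit, so switching may well be related to health. Depending on its sign, the offset could create an apparent benefit or hide a real one.

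What is at stake is modest. These data are meant to give preliminary estimates of the outcome measures, and section 1.4 reports earlier EXCAP effects in older patients with solid tumors of only d = 0.10-0.30. A mode artefact of that size could be taken for an effect, or mask one, when the next trial is planned.

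**Working it through.** **1. The plan's own figures.** Section 8.2.2 enrols 25 and expects 20-30% to withdraw: 25 × (1 − 0.30) = 17.5, in line with the stated minimum of 17 evaluable patients. The exact interval for 12/17 (70.6%) is 44.0-89.7%, which matches the stated 44-90%. Neither figure is in dispute; n = 17 is used below.

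**2. Can a mixed pair occur under the rules as written?**

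| Step | MoCA / MoCA-blind | SPPB / virtual SPPB |
|---|---|---|
| Is one version a substitute for the other? | Yes, stated in 7.2.3.6 | Not stated; 7.2.3.1 says the virtual form is done as well |
| One entry in 9.1, at both visits? | Yes | Yes, one row |
| Can the in-person form be missing at one visit? | Yes, by the substitution rule | Yes, by the safety footnote in 9.1 |
| Tested pre-post in 8.2.2? | Yes, through the geriatric measures (MoCA is not named) | Yes, as physical function |
| Same version required within a pair? | No | No |

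For MoCA every link is in the text. For SPPB the last link, that one score stands in for the other, is only a possible reading.

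**3. Size of the bias.** If k of n pairs switch in one direction and the offset between modes is δ, the mean change is wrong by (k/n) × δ. The documents give neither k nor δ. Assume k = 4 of 17 and δ = 0.5-1.0 SD of the change score:

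- δ = 0.5: 4/17 × 0.5 = 0.12 SD
- δ = 1.0: 4/17 × 1.0 = 0.24 SD

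In raw MoCA points, each point of offset between versions moves the mean by 4/17 = 0.24 points. The documents do not describe the items or scoring of MoCA-blind, so no offset in points can be derived from them.

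**4. False-positive rate.** Simulated two-sided 5% paired t-test, no true change, change-score SD of 1 and n = 17, with the offset δ added only to the pairs that switch:

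| Pairs switching | δ = 0.5 SD | δ = 1.0 SD |
|---|---|---|
| 0 | 5% | 5% |
| 2 | about 5% | about 6% |
| 4 | about 7% | about 11% |
| 8 | about 14% | about 35% |

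**5. After the fix.** With same-version pairs only, the mode bias is 0 and the rate returns to 5%. Dropping 4 mixed pairs leaves 17 − 4 = 13, still above the more than 12 that 8.2.2 relies on. The standard error grows by a factor of √(17/13) = 1.14. With 5 mixed pairs, 12 remain and that threshold is no longer met.

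**The case against.** **Pooling of SPPB and virtual SPPB is not stated.** A reader might infer from the slash and the shared row that the two scores are merged into one variable. The documents do not support that as a fact. Section 7.2.3.1 presents the virtual form as an additional measure, 8.1.1 has staff perform the SPPB and enter its scores, and 8.2.2 uses other headings that plainly cover several instruments. This objection stands, and it limits the SPPB part to a missing specification. It does not reach MoCA, where substitution is explicit.

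**Travel is not a documented trigger.** A reader might also suppose that patients unwilling to travel are switched to the remote versions. Section 7.1 has the coordinator assess them at the affiliated sites and omits only what needs the exercise laboratory. In 9.1 the location footnotes are attached to other tests, not to SPPB or MoCA. Section 7.1 does allow virtual assessment in general. A mainly in-person-to-remote direction is likewise not stated.

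**The inputs are assumed.** The switch share, its direction and the offset have no source in the documents. If switches run both ways, the mean bias partly cancels, though the variance rises. The comparison with d = 0.10-0.30 also assumes a similar SD scale. A higher error rate, 8-16%, would follow if 25% switching were modelled as the same shift in every patient. That overstates the case, because when only some pairs shift the variance also rises.

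**The consequence is small.** These are descriptive outcomes of a single-arm pilot of 25, and without a control arm a change could not be attributed to the intervention anyway. This stands, and it sets the weight of the point. It does not make a mixed pair a valid measure of change.

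**Conclusion.** The point holds as a gap in the analysis rules. It is firm for MoCA: the stated substitution together with the stated paired test permits pairs of different versions. For SPPB and virtual SPPB it is conditional, since the plan leaves open which score is tested and whether the two are kept apart.

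Under the assumed 4 of 17 one-way switchers and an offset of 0.5-1.0 SD, the artefact is comparable in size to the earlier EXCAP effects and the excess of false positives is moderate. If nobody changes mode, the bias is nil. With two switchers the error rate hardly moves, but with eight it is serious.

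Neither feasibility criterion in 8.2.2 uses SPPB or MoCA, so the main conclusion of Aim 2 is safe. This is a desirable clarification rather than a flaw that threatens the study.

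**What to change.** In 8.2.2:

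- List SPPB and virtual SPPB as two separate outcomes, each with its own pre-post test.
- Limit the paired tests of SPPB, virtual SPPB and MoCA to patients with the same instrument or version at both visits. For MoCA, an alternative that keeps all pairs is to score only the items common to both versions, at both visits.
- Record the mode of assessment at each visit, and report the number of mixed-mode pairs for each measure.

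The change is to analysis wording plus one recorded field per visit; no new procedure is needed. The cost is a few pairs and somewhat wider intervals. If virtual SPPB is in fact collected from everyone, separating the two outcomes loses no virtual SPPB pairs.

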8.2.3. Analysis Plan for Exploratory Aim

Descriptive analysis will be used to describe cytokine gene promoter methylation (global % methylation of the gene promoter region and % methylation of each of the identified CpG sites) and gene and protein expression at baseline and post-intervention. Changes from baseline to post-intervention will be compared using paired t-tests. We will use Spearman's correlation to assess relationships between methylation status and gene and protein expression, as well as activity level and clinical measures. We will adjust for multiple comparisons using the Benjamini–Hochberg method.¹¹⁷

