1.0. Background

1.1. Myeloid neoplasms are diseases of aging

MN are a group of diseases that include acute myeloid leukemia (AML), myelodysplastic syndrome (MDS), MDS/myeloproliferative neoplasm (MPN) overlap, chronic myelomonocytic leukemia (CMML), and atypical chronic myeloid leukemia (aCML).¹ Over 60% of MN are diagnosed in adults aged \geq 60 years.^{2,3} For fit older patients with AML (i.e., without significant comorbidities or disabilities), the standard first-line treatment consists of intensive inpatient chemotherapy. Intensive chemotherapy provides the best chance for durable remission, but it is associated with a high treatment-related mortality (60-day mortality: 15-20%).^{4,5} Intensive therapy is utilized in <1% of older patients with AML seen in the community oncology setting, due to various reasons such as distance to tertiary centers and need for hospitalizations.⁶ In the last decade, lowintensity outpatient treatments with reduced treatment-related mortality rates, such as hypomethylating agents (HMA), have become available.^{7–9} These treatments have permitted more older patients with AML, including those with comorbidities and disabilities, to receive leukemia-directed therapy.¹⁰ Furthermore, given the recent FDA approval of HMA combination therapy for AML (e.g., HMA and venetoclax), which has similar or better efficacy than intensive therapy,¹¹ HMA-based therapies will be used more widely in older patients with AML. For older patients with other MN requiring chemotherapy, HMA are often the treatment of choice.¹² Thus, HMA are now standard of care for older patients with MN. HMA are typically given continuously until progression, death, or stem cell transplant.

1.2. Even with HMA, a high percentage of older patients with MN experience physical function decline and symptoms (e.g., fatigue, mood disturbances).

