No mHealth exercise intervention is currently available for older patients with MN receiving outpatient chemotherapy, specifically HMA. TNF α and related cytokines are associated with physical function decline, fatigue, and mood disturbances. Based on our expertise and prior studies, we propose to integrate the content of EXCAP into the PointClick Care app to enhance older patients' adherence to exercise and to understand exercise-induced changes in physical function, fatigue, mood, QoL, and TNF α and related cytokine pathways.

The mobile app and EXCAP have been studied individually in previous studies.^{16,23,33,34,78} In this study, we plan to combine them for older patients with MN receiving outpatient chemotherapy including HMA.

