3.2. Study Type Aim 1: Qualitative study

Aim 2: Single-arm pilot study

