7.0. Treatment Protocol

7.1 Study Outline

Patients who receive HMA and other outpatient chemotherapy typically have declines in their blood counts during the 1st month of therapy before improvements are noted. Therefore, we will initiate our intervention at cycle 2 the earliest. HMA and other common chemotherapy are administered daily as an infusion or subcutaneous injection for 5-10 days every 4 weeks. There are outpatient chemotherapy that are pill-based as well (e.g., enasidenib, ivosidenib) and are also dosed every 4 weeks. We will consent patients and they will complete measures during routine visits. They will complete baseline measures during the 4th week of a chemotherapy cycle up to day 1 of the subsequent cycle prior to chemotherapy administration (study week 0) (Figure 1). The intervention will start during the 1st week of of a new cycle (study week 1) and will last 8 ± 4 weeks. The post-intervention measures will be completed 2 cycles later during the 4th week of the cycle (study week 8 ± 4). To illustrate this, if the intervention starts in cycle 2 week 1, baseline measures will take place on cycle 1 week 4, and postintervention assessment will place on cycle 3 week 4. If the intervention starts in cycle 6 week 1, baseline measures will take place on cycle 5 week 4, and post-intervention assessment will place on cycle 7 week 4.

At the screening visit, we will confirm if the patient is eligible using the eligibility criteria above. Once we confirm their eligibility, we will obtain either in-person or verbal consent. The patient will then complete a demographic questionnaire that asks about the participant's age, gender, race, ethnicity, education level, marital status, employment status, and Eastern Cooperative Oncology Group (ECOG) performance status as well as their cancer and treatment characteristics (see Section 7.2).

For Aim 1, one interview will be conducted with each participant in a private space for approximately 30 minutes. First, we will explain the rationale and demonstrate the use of the GO-EXCAP Mobile App. Second, we will elicit preferences for the content, format, and delivery of the intervention (Table 2). Collectively, the findings will be used to adapt the intervention.

Feature	Goal	Example of Adaptation

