7.2.4. Complete blood count (CBC)

Blood counts measured by standard CBC with differential procedures will be abstracted from the patient's medical record.

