7.4. Assessment of inflammatory markers (Exploratory Aim 2)

Using blood samples, we will assess the blood concentrations of several inflammatory markers. All blood draws will occur in the Wilmot Cancer Center, a UR-affiliated lab, or medical office if needed (in the latter case, we will use a trained study staff member to transport the samples to our storage facility). The location will be selected to minimize subject burden and if possible we will perform blood draws at the same time as a regularly scheduled medical blood draws. The blood will be drawn by trained staff. The time of day will be noted, with future assessments at approximately the same time of day during post-testing. Fasted blood samples (4-6 hours prior to blood with encouragement to maintain hydration) will be drawn. If the blood sample is not fasted, we will still

collect the blood sample and note the last time the person ate in the research record. All subjects will be provided with a \$10 gift card for a café at URMC.

A total of approximately 50 mL of blood (around 4-5 tablespoons) will be drawn at baseline and post-intervention. All tubes will be collected by a study team member, processed, and then transferred to a secured -80°C freezer in lab space maintained by [name] in the Department of Surgery. We will collect the following:

- 1. One red-top tube for serum (9 mL each). This tube will be inverted 10 times, allowed to clot for 30 minutes at room temperature, centrifuged for 15 min at 1600 g and then frozen at -20°C or -80°C. These will be used to assess inflammation (cytokines, etc.).
- Two purple-top EDTA tubes for DNA methylation and plasma analyses (9 mL each, 18 mL total). This tube will be inverted 10 times and allowed to sit at room temp for 30 minutes, centrifuged for 15 min, and then frozen at -20°C or -80°C.
- 3. Two green-top tubes for peripheral blood mononuclear cells (9 mL each, 18 mL total). These will be pre-cooled and processed per SOP. This tube will be inverted 10 times and allowed to sit at room temp for 30 minutes, centrifuged for 15 min, and then frozen at -20°C or -80°C.
- 4. Two paxgene tubes for gene expression analyses (2.5 mL each, 5 mL total). This tube will be inverted 10 times and allowed to sit at room temp for 2-24 hours. Then they will be frozen at -20°C and moved to -80°C for long-term storage.

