Inflammatory cytokines will be assessed using the latest available technology (e.g., *in vitro* enzyme-linked immunosorbent assay; ELISA). These assays will assess the concentration of inflammatory cytokines including TNF α , sTNFR1, sTNFR2, IL-1 β , IL-6, sIL-6R, IL-8, IL-10. Cytokine analyses will be performed at [name] lab.

For DNA methylation analysis, genomic DNA will be isolated from peripheral mononuclear cells with a DNeasy Blood and Tissue Kit (Oiagen) and quantified with the NanoDrop 1000 spectrophotometer. $TNF\alpha$ gene promoter methylation will be quantified using bisulfite pyrosequencing.¹⁰⁷ Briefly, genomic DNA (1000 ng) will be bisulfite converted (converts cytosine to uracil but leaves 5-methylcytosine residues unaffected) using the Epitect Plus Bisulfite Conversion Kit (Qiagen). Using $TNF\alpha$ -specific primers, the region of interest will be amplified by PCR with the PyroMark PCR kit (Qiagen). Pyrosequencing analysis will be used to measure DNA methylation in the $TNF\alpha$ promoter region from -360 to +50 base pairs (containing 12 CpG sites) using the PyroMark Advanced Q24 (Qiagen).¹⁰⁸ We selected these 12 CpG sites based on a prior study which showed that total methylation and methylation at -245 bp correlated with serum TNFa levels.¹⁰⁸ Methylation at -170bp and -120bp also predicted response to a lifestyle behavioral intervention.¹⁰⁸ In addition, the majority of known regulatory transcription factor binding sites (e.g. NF- κ B, Sp-1, Egr1)¹⁰⁹ within the *TNFa* gene promoter region are located in this region. Other cytokine gene promoter methylation will be analyzed as per $TNF\alpha$ (promoter regions will be determined based on previous studies).^{110–112} DNA methylation analyses will be performed at [name] lab.

For gene expression, RNA will be extracted using the RNeasy Mini Kit (Qiagen) according to the manufacter's protocol and quantified using the NanoDrop spectrophotometer.¹⁰⁷ cDNA will be will be prepared by RT-PCR using Superscript IV reverse transcriptase and random hexamers (Invitrogen). qPCR analysis will be conducted using the Applied Biosystems QuantStudio 5 Real-Time PCR system using *TNFa* and cytokine gene-specific primers. Relative expression of *TNFa* and related genes will be calculated using the comparative Ct method, and measurements will be normalized to expression of two reference genes. Gene expression analyses will be performed at [name] lab.

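### The methylation analysis in Section 8.2.3 adjusts only for multiplicity, so the pre-post change cannot be read as an exercise effect and shared cell mix may drive the methylation-expression correlations

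*Combined protocol and SAP*

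**What the plan says.** Section 8.2.3 describes methylation, gene expression and protein expression at baseline and post-intervention, compares the two visits by paired t-test, and uses Spearman "correlation to assess relationships between methylation status and gene and protein expression, as well as activity level and clinical measures". Multiplicity is handled by Benjamini-Hochberg. No term for regimen, cycle, drug exposure or cell composition appears.

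The setting is given elsewhere:

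- **Design.** Section 3.2: "Aim 2: Single-arm pilot study".
- **Drugs.** Section 1.1 introduces low-intensity treatments "such as hypomethylating agents (HMA), have become available" and calls HMA standard of care for older patients with myeloid neoplasms. Section 3.4 admits any outpatient chemotherapy, with HMA as the example, and Section 7.1 mentions pill-based agents.
- **Timing.** Section 7.1: "HMA and other common chemotherapy are administered daily as an infusion or subcutaneous injection for 5-10 days every 4 weeks". The intervention starts at cycle 2 at the earliest. Baseline is in week 4 of a cycle (or up to day 1 of the next, before dosing), and the second assessment is in week 4 two cycles later.
- **Samples.** Section 7.4 says "genomic DNA will be isolated from peripheral mononuclear cells", but its tube list assigns EDTA tubes to DNA methylation and separate green-top tubes to mononuclear cells. RNA comes from other tubes again: "Two paxgene tubes for gene expression analyses".
- **Blood counts.** Section 7.2.4: "Blood counts measured by standard CBC with differential procedures will be abstracted". The schedule in Section 9.1 places this at both visits. No analysis uses it.
- **Intended use.** Section 2.3 asks about relationships among methylation and expression. The summary that closes Section 1 goes further and wants "to understand exercise-induced changes in physical function, fatigue, mood, QoL" and changes in the TNF-alpha and cytokine pathways.

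**The concern.** Two readings are at risk.

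The first is the mean change. Every patient has both exercise and two further treatment cycles between samples, and there is no group with the cycles alone. A significant paired test could reflect drug, disease course, count recovery or exercise. A null result could hide offsetting influences.

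The second is the correlation between methylation and expression. Both are measured in blood samples that mix cell types. If patients differ in cell composition, and composition relates to both measures, a correlation can arise with no regulatory link at the promoter. Benjamini-Hochberg limits chance findings across many tests; it does not remove a bias of this kind.

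Section 1.9 looks ahead to using such biomarkers to tailor exercise prescriptions, and Section 9.3 says results will be published. An unqualified result could carry a wrong biological conclusion into the next study.

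**Working it through.** **Sample size.** Section 8.2.2 anticipates 20-30% withdrawal: 25 × (1 − 0.30) = 17.5, which agrees with its figure of at least 17 evaluable. Its worked interval for 12/17 also reproduces: the Clopper-Pearson limits are 44.0% and 89.7%, against 44-90% in the text. These figures serve the feasibility aim. The exploratory aim has no sample size, effect size or alpha of its own, so n = 17 is assumed here. It could be lower, because the schedule in Section 9.1 allows blood samples to be omitted.

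**Pre-post test with no exercise effect.** Suppose something other than exercise shifts methylation by d standard deviations of the paired difference. The two-sided 5% paired t-test has 16 degrees of freedom and critical value 2.120. Its rejection rate follows from the noncentral t distribution with noncentrality d × √17.

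| Assumed d | Noncentrality | P(significant) |
|---|---|---|
| 0.3 | 1.24 | 21% |
| 0.5 | 2.06 | 49% |
| 0.8 | 3.30 | 87% |

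**Correlation with no direct link.** Let a cell fraction C load on methylation (−λ) and on expression (+λ), the two being otherwise independent. The implied correlation is −λ². Simulated Spearman tests at n = 17, two-sided 5%, per test and before Benjamini-Hochberg:

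| Assumed λ | −λ² | Mean Spearman | Crude rejects | Partial rejects, C measured perfectly |
|---|---|---|---|---|
| 0.3 | −0.09 | −0.08 | 6% | 5% |
| 0.5 | −0.25 | −0.23 | 15% | 5% |
| 0.7 | −0.49 | −0.45 | 47% | 6% |

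**With an imperfect covariate.** A leukocyte differential abstracted from the record is only a proxy for the composition of the assayed cells. At λ = 0.7, partial Spearman on a proxy of assumed reliability 0.6 still rejects about 18% of the time (14-23% for reliability 0.7 down to 0.5). Adjustment helps substantially but is not a cure.

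**Price of adjustment.** The minimum detectable correlation at 80% power is tanh[(1.960 + 0.842)/√(n − 3 − k)] with k covariates. At n = 17 this is 0.63 for k = 0, 0.65 for k = 1 and 0.67 for k = 2.

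**Subgroups.** Section 3.5 reports that 70% of the clinic's older patients with myeloid neoplasms received outpatient HMA. If that carries over, 0.70 × 17 ≈ 12 patients are on HMA and 5 are not. That is too few for anything but description.

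**Data availability.** Section 7.2.2 lists disease type, prior malignancies, cytogenetic risk and regimen, at baseline only. Neither cycle number at baseline nor cycles between samples is named there or in the Section 9.1 schedule. Section 9.5 provides for medical-record review, so both should be obtainable.

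**The case against.** The strongest reply is that the exploratory aim is descriptive. Section 2.3 asks only about relationships, the stated hypothesis concerns feasibility, Section 8.2.3 claims no exercise attribution, and the causal wording sits in the background. That stands, and it limits the stakes. It does not remove the point, because the plan specifies significance tests on quantities that the background proposes to read as exercise-induced.

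The design also has partial protection. The month-1 fall in counts is the stated reason for starting no earlier than cycle 2, and both samples fall around week 4 of a cycle. This matches cycle phase. It does not match cumulative exposure, or any count recovery that continues afterwards. The correction for batch effects in Section 7.5 concerns the banked genome-wide array, not these assays.

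Three stronger readings are tempting, and the documents do not support them.

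- A reader might infer that the drugs lower methylation at this promoter and so work against the rise with exercise described in Section 1.9. That rests on the class name. No passage reports an HMA effect on the TNF-alpha promoter in these cells, or one that keeps accruing after an earlier cycle. Size and direction are both unknown.
- A reader might infer that cell mix certainly changes between visits, or that separate DNA and RNA tubes show it driving both measures. Section 7.1 speaks of counts, not proportions, and separate tubes prove neither.
- A reader might infer that adjusting for the number of HMA cycles would isolate exercise. By design that number is close to two for everyone on HMA, apart from delays, so it is little more than a regimen indicator.

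**Conclusion.** The point holds for interpretation and for the analysis plan; no figure in the plan is wrong. A mean pre-post change in this single-arm study cannot be attributed to exercise, and no covariate adjustment repairs that without a non-exercising group on the same drugs. The crude methylation-expression correlations are open to confounding by cell composition, and that can be reduced with data already scheduled.

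The size depends on inputs that the documents do not give. Over the assumed ranges, the false signal runs from 21% to 87% for the paired test, and from close to nominal (6%) to 47% for the crude correlation. At the low end of cell-mix confounding there is little to correct. The feasibility aim and its conclusions are unaffected, so this is worth changing but is not critical to the trial.

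**What to change.** In Section 8.2.3:

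1. Beside the crude correlations, report partial Spearman correlations adjusted for the lymphocyte/monocyte share from the same-visit CBC differential. Say that this is a proxy, and that it reduces the bias without removing it.
2. State that the mean pre-post change is change over the treatment period and will not be interpreted as exercise-induced.
3. Describe pre-post change separately for HMA and non-HMA regimens, without testing because the groups are small. Abstract cycle number at baseline and cycles between samples from the medical record, and add both to the collected variables.
4. In Section 7.4, reconcile the assignment of EDTA tubes to DNA methylation with the statement that DNA comes from mononuclear cells, so that the cell population behind each measure is known.

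The cost is one degree of freedom in the correlations (minimum detectable correlation about 0.65 instead of 0.63) and a small amount of extra record abstraction. No additional visit or sample is needed.
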